Aim 1: To examine whether high levels of estradiol augment the effect of THC on subjective anxiety, heart rate, blood pressure and salivary cortisol in females. To test this, female occasional cannabis users will receive a single dose of THC (0, 15 mg) during either the early follicular phase (days 1-8) when estradiol levels are low, or during the late follicular phase (days 9-14) when estradiol levels are high. Participants will attend two experimental sessions separated by at least four days, to allow for clearance of the drug. Plasma levels of estradiol, progesterone, and endocannabinoids, as well as salivary cortisol, physiological measures and subjective mood ratings will be obtained at the beginning of all three sessions. During the sessions, physiological measures, subjective ratings of drug effects and mood, and salivary cortisol will be obtained at regular intervals after drug consumption. I hypothesize THC will produce a greater increase in subjective anxiety, heart rate, blood pressure and salivary cortisol during the late follicular phase, and that this will be correlated with higher circulating levels of estradiol.

Aim 2: To examine whether low levels of circulating endocannabinoids augment the effects of THC on subjective anxiety, heart rate, blood pressure and salivary cortisol in females. To test this, the plasma samples mentioned above will also be analyzed for endocannabinoids, anandamide (AEA) and 2-arachidonoylglycerol (2-AG) levels. Baseline AEA and 2-AG levels will be compared to THC-induced increases in subjective anxiety, heart rate, blood pressure and salivary cortisol. I hypothesize females with lower endocannabinoid levels will exhibit greater THC-induced increases in subjective anxiety, heart rate, blood pressure and salivary cortisol levels.

Aim 3: To evaluate determine whether subjective anxiety mediates the physiological stress response after THC. To test this, I will use a multilevel longitudinal mediation model to analyze the collected data. Our independent variables will include within-subjects drug dose and between subjects estradiol (EFG or LFG), AEA and 2-AG levels. Our mediator variable will be subjective anxiety across session time. Our dependent outcome measures include heart rate, blood pressure and salivary cortisol across session time. A multilevel

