For this study we will use a mixed within- and between subject design to examine effects of THC (0 and 15 mg) in two groups of female occasional cannabis users: women tested in the early follicular phase of their menstrual cycle (EFG; N=30) and women tested in the late follicular phase (LFG; N=30). Occasional cannabis users will be defined as individuals who have used cannabis 10 or less occasions in the past thirty days. Females will be randomly assigned EFG or LFG groups. EFG women will be tested 1 to 8 days since the first day of menstruation and LFG women between days 9 and 14. Subjects will attend two four-hour experimental sessions in which they receive THC (15 mg THC) or placebo in counterbalanced order under double blind conditions. Plasma and saliva samples will be obtained before capsule consumption at the start of each session for baseline hormone, endocannabinoid and cortisol levels. The primary outcome measure is salivary cortisol, which will be measured both at baseline and periodically post-drug consumption. Secondary outcome measures include heart rate, blood pressure, body temperature, subjective drug effects (i.e. "feel drug effect"), and THC-induced anxiety. For Aim 1 we will examine THC-induced increases in cortisol in relation to baseline estradiol levels. For Aim 2 will examine THC-induced cortisol in relation to baseline endocannabinoid levels. For Aim 3 we will examine THC-induced increases in heart rate and subjective drug effects relative to THC-

induced increases in cortisol. The study will be approved by the Institutional Review Board at the University of Chicago, in accordance with the Code of Federal Regulations (Title 45, Part 46) adopted by the National Institutes of Health and the Office for Protection from Research Risks of the US Federal Government. The studies will be conducted in accordance with the Helsinki Declaration of 1964 (revised 1989) and the National Advisory Council on Drug Abuse Recommended Guidelines for the Administration of Drugs to Human Subjects.

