Side effects: The drugs used in this study may produce a number of side effects, although most people do not experience any problems at the doses used in this study. Side effects may include abdominal pain, nausea, vomiting, dizziness, feelings of wellbeing, paranoia, sleepiness, abnormal thinking.

Driving or operating machinery: There may be risks to participants if they decided to drive, bike or operate machinery after the session. Therefore, they will not be allowed to drive or bike themselves to the session.

Confidentiality: There may be a risk of loss of confidentiality concerning some of the personal information participants provide to the investigators. As with any study, we will take many precautions to protect participant confidentiality.

Saliva Sample Protocol and Analysis Saliva samples for cortisol analysis will be obtained pre-drug consumption and 1, 1.5, 2, and 2.5 hours post-drug consumption by unstimulated passive drool. Participants will tilt their head forward, allowing the saliva to pool on the floor of their mouth, and then pass the saliva

through the SalivaBio Collection Aid (SCA) into a polypropylene vial. Levels of cortisol in saliva will be measured using a salivary cortisol ELISA kit, a competitive immunoassay specifically designed and validated for the quantitative measurement of salivary cortisol, at the University of Chicago Clinical Research Center.

Plasma Sample Protocol and Analysis

Ovarian Hormone Analysis 5ml blood draws will be obtained while participants are seated and collected in BDVacutainer Gold Top Serum tubes. Samples will be centrifuged at least 30 minutes after collection. The top layer of serum will be collected, aliquoted, and frozen at -80 °C until analyses for hormone levels occur. Plasma estradiol levels will be measured using an ELISA Estradiol (E2) assay. Plasma progesterone levels were measured using the Coat-a-Count Progesterone procedure (Diagnostic Products Corporation).

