Statistical Analyses Sample Size Calculation: Sample size calculations were conducted using G*Power3.1 Software. Since there are no published data on effects of estradiol or eCB levels on response to THC a small effect size was assumed ($d = 0.3$). Recruiting 30 participants for each experimental group, 30 females in early follicular phase, 30 females in late follicular phase, for this study will allow for 80% power to detect an effect at alpha level $p = 0.05$.

A multilevel longitudinal mediation model will be used to analyze the collected data. Our independent variables include within-subjects drug dose and between subjects estradiol (EFG or LFG), AEA and 2-AG levels. Our mediator variable is subjective anxiety across session time. Our dependent outcome measures include heart rate, blood pressure and salivary cortisol across session time. A multilevel longitudinal mediation model will allow for the determination of how drug condition and baseline estradiol, AEA and 2-AG levels affects subjective anxiety across session time, which mediates changes in heart rate, blood pressure and salivary cortisol.

Expected Outcomes Based on several preclinical studies, I expect the LFG to have higher levels of estradiol and anandamide at baseline than the EFG, but no significant differences in baseline trait anxiety, anxiety sensitivity or salivary cortisol (Reed and Carr, 2000; Gorzalka and Dang, 2012; Monero-Lopez et al. 2018). Further, I expect that the effect of THC on subjective anxiety, heart rate and salivary cortisol will be greater in the LFG compared to the EFG, even after including any possible baseline differences in cortisol, trait anxiety or endocannabinoids as a covariate. Additionally, based on preliminary data and prior literature, I expect females with lower endocannabinoid levels, after controlling for cycle phase or estradiol levels, to experience larger increases in subjective anxiety, heart rate and report significantly greater subjective drug and mood effects of oral THC in a dose dependent manner (Hill et al. 2010). Finally, I expect THC-induced change in cortisol to mediate the increase in heart rate and greater subjective drug and mood effects. These results will contribute significantly to the small literature on individual differences in response to THC and lay a foundation for future

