sex-specific cannabis use guidelines, to prevent against THC-induced anxiety, paranoia, and psychosis, and new sex-specific cannabis use disorder treatment options.

Potential problems, Alternative strategies, and Limitations Several problems could arise. First, it may be difficult to recruit qualifying participants in the planned time frame. This seems unlikely since similar inclusion criteria have been used in prior studies within the lab and there has not been significant difficulty recruiting these individuals. But if this is the case, I will increase venues for advertising and identify new online recruitment sources. Second, the differences in responses to THC in females at different phases of their menstrual cycle may be too small to detect with this sample. This is possible, even though we based the sample size on a small effect size. If the findings look promising we would consider increasing our sample size or utilize the data as a pilot for a future study with a larger sample. Third, the two groups of females may differ in pre-capsule measures, such as mood states, cortisol levels, eCB levels, blood pressure or in demographic characteristics such as prior drug use. I will include any of these significant differences between groups as a covariate in the final analyses.

Literature Cited

American Psychiatric Association. (2013). Cautionary statement for forensic use of DSM-5. In *Diagnostic and statistical manual of mental disorders* (5th ed.). doi:10.1176/appi.books .9780890425596.744053

Craft, R. M., & Leitl, M. D. (2008). Gonadal hormone modulation of the behavioral effects of Δ9-tetrahydrocannabinol in male and female rats. *European Journal of Pharmacology*, 578(1), 37–42.

Crean, R. D., Crane, N. A., & Mason, B. J. (2011). An Evidence Based Review of Acute and Long-Term Effects of Cannabis Use on Executive Cognitive Functions. *Journal of Addiction Medicine*, 5(1), 1–8. <https://doi.org/10.1097/ADM.0b013e31820c23fa>

D'Souza, D. C., Ranganathan, M., Braley, G., Gueorguieva, R., Zimolo, Z., Cooper, T., ... Krystal, J. (2008). Blunted Psychotomimetic and Amnestic Effects of Δ-9-Tetrahydrocannabinol in Frequent Users of Cannabis. *Neuropsychopharmacology*, 33(10), 2505–2516. <https://doi.org/10.1038/sj.npp.1301643>

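### The stated 80% power for d = 0.3 with 30 women per cycle-phase group cannot be reproduced; in SD units of the THC-minus-placebo response it is about 21%

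*Combined protocol and SAP*

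**What the plan says.** Under Statistical Analyses, Sample Size Calculation, the protocol reports that G*Power 3.1 was used. Because there are "no published data on effects of estradiol or eCB levels on response to THC a small effect size was assumed", it takes d = 0.3. It then says that recruiting 30 women in each phase group "for this study will allow for 80% power to detect an effect at alpha level" 0.05. Nothing more is given: no test, sidedness, SD to which d is scaled, correlation or number of repeated measurements.

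Other sections indicate what the effect is meant to be:

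- Aim 1: "I hypothesize THC will produce a greater increase in subjective anxiety, heart rate, blood pressure and salivary cortisol during the late follicular phase".
- Expected Outcomes: the "effect of THC on subjective anxiety, heart rate and salivary cortisol will be greater in the LFG compared to the EFG".
- Potential problems, Alternative strategies, and Limitations: it concedes that "the differences in responses to THC in females at different phases of their menstrual cycle may be too small to detect with this sample", and adds that this could happen even though the sample size rested on a small effect.
- Approach: phase is a between-woman factor and THC versus placebo a within-woman factor. "The primary outcome measure is salivary cortisol, which will be measured both at baseline and periodically post-drug consumption". It also says: "For Aim 1 we will examine THC-induced increases in cortisol in relation to baseline estradiol levels".
- Saliva Sample Protocol and Analysis: cortisol samples are "obtained pre-drug consumption and 1, 1.5, 2, and 2.5 hours post-drug consumption".

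**The concern.** Thirty per group is far too few for a between-group comparison to detect 0.3 SD with 80% power, so the claim looks wrong on sight. The phase difference in THC response is a between-group comparison of within-woman differences. The within-woman design helps only through the correlation between sessions, and the plan assumes no value for it.

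This paragraph is the only justification for the sample size. A reader who accepts 80% power for a small effect could take a null phase result as evidence against one. In SD units of the THC-minus-placebo response, an observed difference of zero would carry a 95% interval of about -0.52 to +0.52. That interval excludes 0.74 but not the assumed 0.3.

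**Working it through.** **Inputs.** From Sample Size Calculation: d = 0.3, 30 per group, alpha 0.05, stated power 80%. The contrast is inferred from the sections listed above: the phase difference in the THC-minus-placebo response. Sidedness and SD unit are not stated, so both sidednesses and both natural units are tried. All correlations below are assumptions.

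**1. Attempt to reproduce the 80%: d in SD units of the THC-minus-placebo response.** Two-sample t-test on one difference per woman, 58 df, noncentrality d × √(n/2) = 0.3 × √15 = 1.162. The critical values are 2.002 (two-sided) and 1.672 (one-sided).

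| | Two-sided | One-sided |
|---|---|---|
| Power at d = 0.3, 30 per group | 20.8% | 31.0% |
| n per group for 80% at d = 0.3 | 176 (175 gives 79.9%) | 139 (138 gives 79.98%) |
| d with 80% power at 30 per group | 0.736 | 0.650 |

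The 95% interval half-width is 2.002 × √(2/30) = 0.517 SD.

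**2. Continuous baseline estradiol instead of phase group.** With the equal-split conversion, r = d/√(d² + 4) = 0.3/√4.09 = 0.148. At N = 60, power is about 20% two-sided and 30% one-sided.

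**3. Overall THC effect in all 60 women.** This is not the phase question. A paired t-test with standardised mean difference 0.3 and N = 60 gives 62.8% two-sided and 74.3% one-sided.

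**4. d in single-session SD units, one value per session.** With between-session correlation ρ, the difference has SD √(2(1 − ρ)), so the effective d is 0.3/√(2(1 − ρ)).

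| Assumed ρ | Power, two-sided | Power, one-sided | Difference with 80% power, two-sided |
|---|---|---|---|
| 0 | 12.7% | 20.2% | 1.04 |
| 0.3 | 16.2% | 25.0% | 0.87 |
| 0.5 | 20.8% | 31.0% | 0.74 |
| 0.7 | 31.4% | 43.6% | 0.57 |
| 0.8 | 43.9% | 56.8% | 0.47 |
| 0.9 | 72.4% | 82.2% | 0.33 |

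Power reaches 80% at ρ = 0.917 two-sided (0.893 one-sided). The 95% half-width is 0.517 × √(2(1 − ρ)), which falls below 0.30 only above ρ of about 0.83.

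**5. Mean of the four post-dose cortisol samples, same unit.** With within-session correlation w and between-session correlation b, the contrast variance is 2(1 + 3w)/4 − 2b. At w = 0.8, b = 0.5 this is 1.70 − 1.00 = 0.70, and two-sided power is 28%. At (0.7, 0.7) it is 1.55 − 1.40 = 0.15, and power is 84%. At (0.8, 0.8) it is 0.10, and power is 95%. For 80% two-sided, b must be 0.54, 0.62, 0.69, 0.77 or 0.84 at w = 0.5, 0.6, 0.7, 0.8 or 0.9. Samples from different sessions must therefore correlate almost as strongly as, or more strongly than, samples within one session.

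**6. G*Power repeated-measures ANOVA, within-between interaction.** N = 60, noncentrality f² × N × m/(1 − ρ).

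- Two measurements, f = d/2 = 0.15: 62.8% at ρ = 0.5, and 80% at ρ = 0.667. Here f = 0.15 is a difference of differences of 0.6 SD, twice the stated d.
- Two measurements, 0.3 SD correctly scaled as f = 0.075: 20.8% at ρ = 0.5, identical to step 1.
- Four or five measurements, f = 0.15, ρ = 0.5: 78.6% or 84.4%, for a group-by-measurement test with 3 or 4 numerator df.

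**The case against.** The strongest reply is that the plan never says its effect is the phase difference, nor that d is in SD units of the THC-minus-placebo response. In single-session units the calculations above run from 13% to 95% two-sided, depending on correlations and averaging, so a true power of 21% has not been shown. This stands. The 21% is conditional on the unit, and the firm finding is that the 80% cannot be reproduced from what is written.

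A second reply is that ordinary G*Power runs do land near 80%: the four- or five-measurement interaction above, or 0.3 entered as f in a between-factor test with three measurements at correlation 0.5, which gives 79.9%. A time-course test is not foreign to a plan that analyses outcomes over the session. These runs may explain where the figure came from, but they do not rescue it. The first tests group by time and ignores drug. The second corresponds to a 0.6 SD difference between groups. Both need inputs that the plan does not give.

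Third, the r = 0.148 conversion treats estradiol as a two-group label. If phase were a median split of a normally distributed level, r would be about 0.19 and two-sided power about 30%. That is fair, but still far from 80%.

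Finally, the limitations section already warns that the phase difference may be undetectable. The warning tempers the claim but leaves the 80% uncorrected and repeats the small-effect premise.

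**Conclusion.** The concern holds. For the phase difference in THC response, the stated inputs do not give 80% power. In SD units of the THC-minus-placebo response the shortfall is 80 − 21 = 59 percentage points two-sided, or 80 − 31 = 49 one-sided. This rests on two inferences: that the phase contrast is the one intended, and that d is scaled to the SD of one difference score per woman. Changing the unit can bring power to 80%, but only with a between-session correlation near 0.9 for single values, or correlations close to or above the within-session value for averaged samples. The plan states neither. The 80% may come from an undocumented calculation. As the only support for 60 women, it needs correcting or documenting.

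**What to change.** In Sample Size Calculation, name the contrast, test, sidedness, SD unit, assumed between-session correlation (and within-session correlation if samples are averaged) and number of measurements. Replace the 80% statement with, for example:

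> In a simple two-group comparison of one THC-minus-placebo difference per woman, with 30 women per group and a two-sided 0.05 test, power is 80% for a phase difference of 0.74 SD of that difference and about 21% for 0.3 SD.

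If a one-sided test was intended, the matching figures are 0.65 SD and 31%. If the 80% came from another test, state that test, its inputs and the effect it corresponds to.

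In the limitations section, keep the small-effect remark but qualify it, for example:

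> A small effect (d = 0.3) was assumed, but in a simple two-sided comparison of one difference score per woman, 30 women per group give 80% power only for a phase difference of about 0.74 SD of the THC-minus-placebo response.

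This costs wording only, with no extra women, visits or assays. The price is a less favourable stated figure. Keeping 80% two-sided at d = 0.3 in this unit would need 2 × 176 = 352 women, 292 more than planned, which is not proposed.

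### Aims 1 and 2 ask whether estradiol and endocannabinoids change the THC effect, but no coefficient is named as the test, and the mediator differs between sections

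*Combined protocol and SAP*

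**What the plan says.** All references are to the combined protocol and SAP.

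- **Aim 1** is worded as follows: "To examine whether high levels of estradiol augment the effect of THC on subjective anxiety, heart rate, blood pressure and salivary cortisol in females".
- **Aim 2:** "To examine whether low levels of circulating endocannabinoids augment the effects of THC", with the comparison described as: "Baseline AEA and 2-AG levels will be compared to THC-induced increases in subjective anxiety, heart rate, blood pressure and salivary cortisol".
- **Approach:** "The primary outcome measure is salivary cortisol". The first two aims are restated as "For Aim 1 we will examine THC-induced increases in cortisol in relation to baseline estradiol levels" and "For Aim 2 will examine THC-induced cortisol in relation to baseline endocannabinoid levels". On sampling: "Plasma and saliva samples will be obtained before capsule consumption at the start of each session".
- **Statistical Analyses:** one model is given, a multilevel longitudinal mediation model. "Our independent variables include within-subjects drug dose and between subjects estradiol (EFG or LFG), AEA and 2-AG levels". Anxiety is the mediator; heart rate, blood pressure and cortisol are outcomes. Aim 3 gives the same structure.
- **Expected Outcomes:** predicts a larger THC effect in the late follicular group (LFG) than in the early follicular group (EFG), and higher anandamide in the LFG. It intends control for phase or estradiol when endocannabinoids are studied. It also expects the cortisol change to mediate heart rate and subjective effects.
- **Potential problems, Alternative strategies, and Limitations:** pre-capsule differences become covariates if they are significant between groups.

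**The concern.** Whether a moderator augments a drug effect is answered by a drug-by-moderator contrast. The plan has what is needed to form one (a placebo session, a pre-capsule sample in each session, two phase groups) but does not say which coefficient answers Aim 1 or Aim 2. Several analyses fit the wording, and they estimate different things.

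The outcome equation of a mediation model also conditions on anxiety, so its coefficients show only the part of an effect that anxiety does not carry. AEA and 2-AG are treated as between-subject variables although blood is drawn at both sessions, and the value to use is not stated. Estradiol appears both as the EFG/LFG group and as a measured baseline level.

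With the contrast and the mediator both open, either could be settled after the results are seen, and this affects the primary outcome.

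**Working it through.** **The plan's own figure.** Statistical Analyses gives 80% power for d = 0.3 with 30 per group at alpha 0.05. A two-sided two-sample t-test with those inputs has 20.8% power; a paired test on 60 women has 62.8%. A repeated-measures F-test with f = 0.15, four measurements and correlation 0.5 reaches 78.6%, but the plan states neither the measurement count nor the correlation. The 80% therefore cannot be tied to either aim.

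**Assumed inputs for the rest** (none is in the documents): outcome SD 1; between-session correlation r_b 0.3-0.7; within-session correlation r_w 0.5-0.8, never below r_b; 30 v 30; two-sided 0.05.

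**1. Additive fit, true augmentation 0.3 SD on THC only.** The phase coefficient averages the two sessions: (0 + 0.3)/2 = 0.15. If the pre-capsule sample is one of the five time points, it is 0.3 x 4/5 x 1/2 = 0.12. The drug x phase coefficient is 0.30. If anxiety carries half the augmentation, drug x phase given anxiety is about 0.15.

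**2. Additive fit, no augmentation, the same phase difference of 0.2-0.5 SD in both sessions.** The shift enters the phase coefficient in full. Simulated rejection, one post-dose value per session:

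| Analysis | Rejects |
|---|---|
| Phase term, baseline covaried only if significant | about 5-26% |
| Phase term, baseline always covaried | about 5-19% |
| Drug x phase (THC minus placebo) | about 5% |

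**3. Post minus pre in the THC session, no augmentation.** Suppose the afternoon change differs by phase by g in both sessions. The standardised difference is g/√(2(1 − r_w)).

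- g = 0.2: 0.2/√1.0 = 0.20 to 0.2/√0.4 = 0.316; simulated rejection 11.4-22.8%.
- g = 0.3: 0.30 to 0.474; simulated rejection 20.8-44.8%.
- THC minus placebo: about 5%, because the drift is in both sessions and cancels.

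**4. Aim 2.** Let AEA be higher in the LFG by g within-phase SDs, drug x phase be 0.3 SD, and the true slope of the THC effect be −0.15 per SD of AEA. Omitting phase from the analysis of the effect adds 0.3 x (g/4)/(1 + g²/4) = 0.3g/(4 + g²):

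- g = 0.3: −0.15 + 0.09/4.09 = −0.128
- g = 0.5: −0.15 + 0.15/4.25 = −0.115
- g = 0.8: −0.15 + 0.24/4.64 = −0.098

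Regressing a change score on AEA with phase as a plain covariate recovers −0.146 to −0.149. In a stacked model of THC and placebo records, a phase main effect leaves the drug x AEA slope unchanged; adding drug x phase restores −0.15.

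**5. Power of the interaction for 0.3 SD.** With one value per session and no baseline adjustment, d = 0.3/√(2(1 − r_b)) = 0.254, 0.300, 0.387 for r_b = 0.3, 0.5, 0.7, giving 16%, 21% and 31%. The drug main effect in 60 women gives 49%, 63% and 84%. The mean of four post-dose samples adjusted for the pre-capsule value gives 34-83% in simulation; the top needs no session-level variance and independent residuals.

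**6. Mediation direction.** Aim 3 and the model run from anxiety to heart rate, blood pressure and cortisol. Expected Outcomes runs from cortisol to heart rate and subjective effects. Approach restates Aim 3 by relating heart rate and subjective effects to cortisol, without a direction.

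**The case against.** The strongest reply is that the interaction is already there in words. Expected Outcomes predicts a larger THC effect in the LFG, and in a placebo-controlled within-subject design that is naturally drug x phase. This stands as far as it goes. A reader might infer that the plan rules out interactions or takes the phase main effect as the Aim 1 test; the documents say neither. But a prediction in words names no coefficient.

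Four further limits stand:

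- A reader might infer that the intended control for phase fails in Aim 2. It does not if a change score is regressed on endocannabinoids plus phase, which is a natural reading of Aim 2 and Approach. It fails only in a stacked model without drug x phase.
- A reader might infer that the diurnal fall in cortisol by itself biases the comparison. A fall common to both groups cancels between LFG and EFG, and fixed session hours address it. Only a phase-specific course does harm, and the documents give no figure for one.
- Expected Outcomes mentions baseline differences as covariates without a significance trigger, which brings the 26% down to about 19%. It also expects no baseline cortisol difference, so the larger shifts are extremes.
- A mediation analysis can also report total and indirect effects, so conditioning on anxiety matters only if the outcome-equation coefficients are read as the tests.

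The mediator conflict rests on one sentence and a directionless restatement set against consistent text elsewhere. It is a wording repair, but it concerns the primary outcome.

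**Conclusion.** The point holds as a failure to specify, and should be fixed. No coefficient is designated as the test of Aim 1 or Aim 2, *THC-induced* has two readings, and the model fitted literally as listed answers neither aim. The halving of the augmentation and the full entry of a common phase difference are algebra. The rejection rates (about 5-26%, or 5-19% with baseline always covaried, and about 11-45%, against about 5%) are hypothetical illustrations: they depend on assumed correlations, shifts and drifts, and on fits the plan permits but does not prescribe. They do not show that the planned analysis has an inflated error rate. The conflict over cortisol's role is plain in the text and needs no assumption.

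**What to change.** 1. **Aim 1.** Define the THC effect as THC minus placebo. Name drug x phase (LFG versus EFG), in a model without anxiety, as the test for cortisol. Always adjust for that session's pre-capsule cortisol, replacing the significance-triggered rule.
2. **Aim 2.** Test drug x AEA and drug x 2-AG with drug x phase in the same model. Equivalently, regress the THC-minus-placebo change on AEA and 2-AG with phase as a covariate, handling baseline the same way. Use one defined value per woman for AEA, 2-AG and estradiol, for example the mean of the two pre-capsule samples.
3. **Aim 3.** State anxiety to physiology as the one primary mediation direction, reconcile Approach and Expected Outcomes with it, and label any model with cortisol as mediator exploratory.
4. **Power.** State that the figure refers to the interaction, with the correlation and number of samples assumed. For 0.3 SD it is 16-31% with one unadjusted value per session, and 34-83% for the baseline-adjusted mean of four samples.

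The cost is a few model terms, some wording and a less favourable stated power. No new data or procedures are needed.
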